6.13.2 Time to Clinical Failure

As with TtCW, subjects who did not experience a clinical worsening and who did not receive at least 24 weeks of treatment will be censored at their last study visit.

The TtCF (in days) will be analyzed using the SAS procedure LIFETEST to calculate the log-rank statistic and p-value to compare treatment groups. The analysis statement will be of the form:

```
proc lifetest data= set plots=survival;  
  time TtCF * status(0);  
  strata treprostинil_use / group=treatment test=logrank;  
  run;
```

A Cox model, with baseline treprostинil use as a covariate, will be used to estimate the hazard ratio and its 95% CI.

Graphical displays, including Kaplan-Meier curves, and tabulations of TtCF and the individual components and the composite endpoint will be presented by treatment group.

Supportive and sensitivity analyses similar to those planned for TtCW will be conducted.

6.13.3 Worsening from Baseline of WHO Functional Class at Week 24

The WHO defines four functional classes for patients with PAH. In order to enter this trial, subjects had to be in Class III or IV. For the purpose of analysis of worsening WHO functional class, the WHO categorization will be augmented with a fifth class, death. At Week 24, each subject will be classified as improved, unchanged, or worsened from baseline. Those who die will be classified as worsened.

Multiple imputation will be used to impute those who are still alive but do not have a measurement of WHO Functional Class at Week 24. Predictor variables will be baseline and Week 12 WHO class, 6MWT, and Borg score. Imputation of missing data for subjects in either treatment group will be based on subjects in the placebo arm to minimize assumptions of missing at random for the treated group. One hundred datasets will be imputed and SAS PROC MIANALYZE will be used to compare the treatment groups with respect to the proportion of worsening from baseline in WHO Functional Class at Week 24 using Cochran-Mantel-Haenszel statistics stratified by baseline inhaled treprostинil use.

Summaries will include the rates by treatment, test statistic, p-value, and the odds ratio.

6.14 Other Secondary Analyses

The study has the following other secondary outcomes:

- Outcomes at 12 weeks change from baseline in the following:
 - 6MWT
 - WHO Functional Class

- Borg Dyspnea Score
- NT-pro-BNP levels
- Outcomes at 24 weeks change from baseline in the following:
 - Borg Dyspnea Score
 - NT-pro-BNP levels
- Total mortality (censored if lost to follow up)

6.14.1 **Change from Baseline in 6MWT at Week 12**

The model used to test the 6MWT at Week 24 (see Section 6.13.1) will be applied to Week 12; however, the contrast at Week 12 will be used instead of the contrast at Week 24.

6.14.2 **Worsening from Baseline in WHO Functional Class at Week 12**

The method described in Section 6.13.3 will be used to analyze the data at Week 12 substituting the phrase “Week 12” for “Week 24”. For the multiple imputation, only baseline variables will be used.

6.14.3 **Change in Borg Dyspnea Score at Weeks 12 and 24**

The Borg Dyspnea Score is an 11 point scale measuring the degree of dyspnea from 0, or “nothing at all”, to 10, or “panic level”. Descriptive statistics of the raw and change from baseline values for Borg Dyspnea Score will be presented for each scheduled visit by treatment group. A score of 11 will be assigned to subjects who died. The Borg score will be treated as a continuous variable.

A longitudinal model will be used to describe the change from baseline in Borg score over time. Contrasts will be calculated at Weeks 12 and 24 to compare the treatment groups with respect to change. The outcome variable will be change from baseline. Independent variables will be treatment, inhaled treprostinil use baseline Borg, visit number, and the interaction of visit and treatment.

Multiple imputation, assuming that patients who stop study medication will adopt the experience in the placebo group, will be used to account for missing data. An addendum to this protocol, to be written before the data are unblinded, will present the SAS program to be used for the multiple imputation.

Sensitivity analyses will explore the extent to which multiple imputation of Week 24 data influences the interpretation of the outcome. One sensitivity analysis will assume that all subjects without Week 24 data would have continued on their assigned treatment through the end of the study; another sensitivity analysis use the longitudinal model described above without any imputation for missing data. Other planned sensitivity analyses will be described in an addendum to this SAP, which will be completed after the Blind Data Review.

6.14.4 NT-pro-BNP at Weeks 12 and 24

Descriptive statistics of the raw values and changes from baseline NT-pro-BNP will be presented for each scheduled visit by treatment group. Because the parameter is highly skew, the data will be log-transformed before analysis. A longitudinal model will be used to describe log NT-pro-BNP over time. The outcome variable will be the value at each time of measurement, not the change from baseline. Independent variables will be treatment, inhaled treprostinil use, baseline log NT-pro-BNP, visit number, and the interaction of visit and treatment. Contrasts will be calculated at Weeks 12 and 24 to compare the treatment groups with respect to level of the parameter.

These contrasts will be on the log scale. In order to provide summary statistics that are easily clinically interpretable, the estimates may be back transformed to the natural scale and the change from baseline may be calculated as the difference between the mean of the back-transformed estimates and the mean of the baseline value.

Multiple imputation, assuming that patients who stop study medication will adopt the experience in the placebo group, will be used to account for missing data. An addendum to this protocol, to be written before the data are unblinded, will present the SAS program to be used for the multiple imputation.

Sensitivity analyses will explore the extent to which multiple imputation of Week 24 data influences the interpretation of the outcome. One sensitivity analysis will assume that all subjects without Week 24 data would have continued on their assigned treatment through the end of the study; another sensitivity analysis use the longitudinal model described above without any imputation for missing data. Other planned sensitivity analyses will be described in an addendum to this SAP, which will be completed after the Blind Data Review.

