5.1.3 Other Secondary Endpoints (Stage 3)

The study has the following other secondary outcomes:

- Outcomes at 24 weeks – change from baseline in the following:
 - Borg Dyspnea Score
 - NT-pro-BNP levels
- Total mortality (censored at last contact if lost to follow-up or if vital status is missing at study termination)

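### The optional model-based NT-pro-BNP change from baseline in SAP 6.14.4 mixes scales, so it shows a fall in both arms when nothing has changed

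*SAP*

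**What the plan says.** SAP section 5.1.3 lists change from baseline in "NT-pro-BNP levels" at 24 weeks among the Stage 3 endpoints. Section 6.14 adds the same measure at 12 weeks.

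Section 6.14.4 sets out the analysis in this order:

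- Descriptive statistics of raw values and raw changes from baseline are to be presented for each scheduled visit, by arm. This is a firm commitment.
- "Because the parameter is highly skew, the data will be log-transformed before analysis".
- "The outcome variable will be the value at each time of measurement, not the change from baseline". The covariates include "baseline log NT-pro-BNP, visit number, and the interaction of visit and treatment".
- Treatment groups are compared by contrasts at Weeks 12 and 24. "These contrasts will be on the log scale".
- To give clinicians a readable summary, the model estimates may optionally be exponentiated. The section then permits a change figure, defined by this subtraction: "the difference between the mean of the back-transformed estimates and the mean of the baseline value".

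The last item is permissive. The section gives no retransformation correction (variance term or smearing). It does not say that the baseline mean is taken on the log scale, or whether it is taken per arm or over both arms. Section 6.3.2 gives the general definition of change: post-baseline minus baseline of the original measurements.

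**The concern.** The two terms of the subtraction appear to be different kinds of average. The first comes from a model for log values, so exponentiating its LS mean gives a geometric mean. The second is described only as the mean of the baseline value. The same section names the log explicitly when it means log baseline, so the natural reading of this term is the ordinary mean of raw baseline values.

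For positive values that vary, the geometric mean is always below the arithmetic mean. If the distribution at Week 24 were the same as at baseline, the formula would still give a negative number, in the placebo arm as well as the active arm.

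What is at stake is how the result is read. This is the only model-based change figure offered for an endpoint that section 5.1.3 defines as a change, and it is included to be easy to interpret clinically. A report could show almost no change in the raw descriptive table and a clear fall in the model-based one.

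**Working it through.** **Inputs.** The SAP states no SD, mean or effect size for NT-pro-BNP, so there is no planned figure to reproduce. From SAP 6.14.4: log-scale model, log baseline as covariate, and the change formula. From SAP 4.1: 120 subjects per group, used only in the simulation. Assumed, because the documents do not give them: log-normality; SD of log NT-pro-BNP, s, from 0.3 to 1.5; a baseline-to-visit correlation of log values of 0.8; and a baseline arithmetic mean of 1000 arbitrary units.

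**Reading A: the estimate is the exponentiated LS mean.** For a log-normal variable, arithmetic mean = geometric mean × exp(s²/2). With no true change, the apparent change as a share of the baseline arithmetic mean is exp(−s²/2) − 1.

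**Reading B: the estimate is the average of exponentiated subject-level fitted values.** The variance lost is the residual part, s²(1 − ρ²). The apparent change is exp(−s²(1 − ρ²)/2) − 1. With ρ = 0.8, 1 − ρ² = 0.36.

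| s | Reading A | Reading B (ρ = 0.8) |
|---|---|---|
| 0.3 | −4.4% | −1.6% |
| 0.5 | −11.8% | −4.4% |
| 0.8 | −27.4% | −10.9% |
| 1.0 | −39.3% | −16.5% |
| 1.2 | −51.3% | −22.8% |
| 1.5 | −67.5% | −33.3% |

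For example, at s = 1.0: A gives exp(−0.5) − 1 = −39.3%, and B gives exp(−0.18) − 1 = −16.5%.

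**Simulation check.** The simulation used 2000 runs, 120 per arm, ANCOVA of the log visit value on arm and log baseline, and no true change. It covers a single visit and leaves out the repeated-measures structure and the multiple imputation. Mean apparent change per 1000 units of baseline:

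| s | Placebo (A) | Active (A) | Placebo (B) |
|---|---|---|---|
| 0.5 | −116 | −116 | −43 |
| 0.8 | −271 | −275 | −107 |
| 1.0 | −391 | −393 | −162 |
| 1.2 | −512 | −509 | −226 |

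This agrees with the closed forms, and the offset is about equal in the two arms. The active-to-placebo ratio from the log-scale contrast stayed within −0.1% to +0.8% of 1.

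**What the offset can hide.** Suppose the geometric mean truly rises by 20%. Reading A then gives 1000 × (1.2 × exp(−s²/2) − 1): +59 at s = 0.5, −129 at 0.8, −272 at 1.0 and −416 at 1.2. The formula turns positive only when the true rise exceeds exp(s²/2) − 1, which is 13% at s = 0.5, 38% at 0.8 and 65% at 1.0.

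**With both terms on one scale.** In the same simulation, the exponentiated LS mean divided by the pooled geometric mean at baseline was within +0.1% to +0.2% of no change. Arithmetic mean minus arithmetic mean was within −0.7 to +0.9 per 1000.

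**The case against.** The strongest reply is that little depends on this sentence. The summary is optional. The formal comparisons are made on the log scale and are untouched. The endpoint is in Stage 3, tested only if Stages 1 and 2 succeed. The same section commits to a table of raw changes, which is on a consistent scale. Section 6.2 already plans an addendum on data conventions before unblinding, where the wording could be settled. All of this stands, and it limits the point to a minor one.

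It can also be said that the SAP never uses the words geometric or arithmetic, and that a mean of several back-transformed estimates is odd wording for a single LS mean. That is fair. Under Reading B the bias is smaller, but it remains. The size under either reading depends on an SD that the documents do not give; at s = 0.3 it is only a few per cent.

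Three stronger readings are tempting, and the documents do not support them:

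- A reader might infer that this is the only change-from-baseline figure for NT-pro-BNP. It is the only model-based one; the raw-change table is also planned.
- A reader might infer that the figure must come out negative. Only the offset is negative, and a large enough true rise gives a positive result.
- A reader might infer that the treatment comparison is biased. It is not: the contrast does not use this formula, and with balanced baselines the offset is about the same in both arms.

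The permissive wording does not repair the formula. If the summary is produced, this is the only rule given for it.

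**Conclusion.** The point holds in a limited form. As written, the optional model-based change from baseline puts its two terms on different scales and is biased downward in both arms. The direction under Reading A follows from the log model, the skewness the SAP itself states, and the natural reading of the baseline term; it needs no outside figure. The size rests on log-normality and an assumed s: a spurious fall of about 4% to 68% of the baseline arithmetic mean for s from 0.3 to 1.5. Under Reading B, with a correlation of 0.8, the fall is about 2% to 33% over the same range.

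The harm is confined to the within-arm change on the natural scale, which could contradict the raw table in the same report. The tests, p-values and log-scale treatment effect are not affected. Severity is minor.

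**What to change.** Replace the last sentence of the back-transformation paragraph in SAP 6.14.4 with:

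> For each arm, report the geometric-mean ratio to baseline, exp(LS mean of log value minus the pooled mean log baseline at which the LS means are evaluated), with 95% CI; between arms, report exp(contrast) with 95% CI.

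The pooled mean must be named. LS means are adjusted to a common baseline, so dividing by each arm's own baseline would let chance imbalance into the ratios, and the two arms' ratios would no longer divide to exp(contrast).

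The cost is one sentence, in the SAP or in the addendum planned before unblinding. It needs no new data and no change to the model or the tests.

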6.14.5 Total Mortality

Vital status will be assessed for each randomized subject through the end of the study. All subjects who discontinue the study, either for premature termination or for meeting a primary endpoint of clinical worsening, will continue to be followed, to the extent possible, for vital status until the sponsor concludes the study. Subjects who are lost to follow-up will be censored at the date known alive. The total mortality (all cause death) in the two treatment groups will be evaluated with a Cox regression analysis to provide an estimated hazard ratio and corresponding 95% CI.

Time-to-death analyses will use the following SAS code with different rules for the variable *status(0)*.

```
proc lifetest data= set plots=survival;
  time TtCW * status(0);
  strata treprostinil_use / group=treatment test=logrank;
  run;
```

Deaths are categorized as Cardiovascular related, PAH related, and other. A table will show the proportion of deaths, by treatment arm, in each category. Sensitivity analyses for this table will be described in an addendum to this SAP, which will be completed after the Blind Data Review.

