Vital status will be assessed for all randomized subjects at the formal conclusion of the study. For randomized subjects who terminate early, vital status will be assessed three months following discontinuation unless the formal conclusion of the study occurs within the three month time period. Study site personnel will record vital status information in source documents and record relevant information on appropriate CRFs.

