6.4.2 Handling of Missing Data

The sponsor acknowledges the implications of missing data on the integrity of study outcomes and, consistent with Fleming's recommendations (2011), implemented the following strategies to minimize the extent of missing data:

1. All subjects were allowed to continue in the study until the close of study, whether on IMP or not. Subjects were not to be summarily discontinued from the study, unless 1) the subject withdrew informed consent; 2) the subject met a primary endpoint and declined continuation in the study; or 3) the subject continued to be non-adherent to study protocol after repeated attempts to correct (at least 6 months). However, the subject has the right to discontinue from the study at any time. All subjects who discontinue the study, unless they withdraw informed consent, will continue to be followed, to the extent possible, for vital status until the sponsor concludes the study.
2. Recent publications (Sitbon et al., 2015; Galiè et al., 2015) have shown that roughly 20% of subjects prematurely terminate from mortality and morbidity studies in PAH. The sponsor has throughout the study engaged with study investigators to encourage subjects' retention in the study, adherence with the protocol, and compliance with IMP.
3. While the study protocol is necessarily complex in order to obtain the scientific data to evaluate the safety and efficacy of the IMP, the sponsor designed the protocol in the manner that was not burdensome to the subjects: 1) Much of the data collected for secondary endpoints is derived from assessments performed for 'standard of care' visits; 2) Study visits are minimal (quarterly) with permissive visit windows (\pm 10 days); 3) Use of optional substudies for exploratory endpoints; and 4) Sponsor-provided Tyvaso to all subjects in the study.

Methods for handling missing data will be described in the sections discussing each outcome.

No imputation is planned for missing safety or exploratory data.

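### The total-mortality program in SAP 6.14.5 uses time to clinical worsening as its time variable, and no status rule can turn that into total mortality

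*SAP*

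**What the plan says.** **The program.** SAP 6.14.5 states "Time-to-death analyses will use the following SAS code with different rules for the variable" status(0). The time statement that follows begins "time TtCW * status(0" and matches the one in the primary analysis (SAP 6.12.6). No status rule is given, and no change to the time variable is mentioned.

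**What TtCW measures.** SAP 5.1.1 ends TtCW at the first worsening event confirmed by the adjudication committee. SAP 6.12.6 censors subjects without an event at their last study visit.

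**What the text says about mortality.**
- SAP 6.14.5 follows vital status to the end of the study, including after a primary event. It adds: "Subjects who are lost to follow-up will be censored at the date known alive".
- SAP 5.1.3: "Total mortality (censored at last contact if lost to follow-up or if vital status is missing at study termination"). SAP 6.14 has a shorter form: "Total mortality (censored if lost to follow up").
- SAP 6.4.2: subjects who leave the study, "unless they withdraw informed consent, will continue to be followed, to the extent possible, for vital status until the sponsor concludes the study".
- Protocol 7.14: "Vital status will be assessed for all randomized subjects at the formal conclusion of the study".

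**Its role.** Total mortality is listed in SAP 5.1.3, so it is formally tested in Stage 3 (SAP 6.10.3). SAP 6.14.5 also says: "The total mortality (all cause death) in the two treatment groups will be evaluated with a Cox regression analysis", to give a hazard ratio and confidence interval. No Cox code is printed.

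**The concern.** The program and the text describe different quantities. Non-fatal worsening will be common: the trial runs to 113 worsening events, and SAP 6.12 notes that subjects need not leave the study after one. Many subjects will therefore have a TtCW that stops well before their death or their last contact.

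The time-to-clinical-failure program in SAP 6.13.2 did have its time variable changed to TtCF. That points to a copying slip in 6.14.5 rather than a convention.

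At stake is the validity of a formally tested mortality comparison and its survival plot. Stage 3 is reached only after a significant primary result (SAP 6.10.1), which is when follow-up on TtCW is likely to differ between arms.

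**Working it through.** **1. What a status rule can do.** Take a subject hospitalised for PAH at month 4 who dies at month 20, and another hospitalised at month 4 who is alive at close. Both have a TtCW of 4 months.
- *All-deaths rule* (status = 1 for anyone who died): the first is timed as dying at month 4, and the second is censored at month 4 although known alive later.
- *First-event rule* (status = 1 only if death was the first event): the first subject's death is dropped, and worsening becomes a censoring event.

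Neither is time to death.

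**2. Inputs.** From SAP 4.1: one-year worsening 45% versus 25%, 120 per arm, 1.5 years' accrual, 2.5 years in total. The worsening rate is read as including death. The documents give no mortality design figure, no death rate for this population and no worsening–death correlation. Assumed death hazards are 0.05, 0.10 and 0.1625 per year. The last equals −ln(0.85), from the 15% first-year mortality after diagnosis in Protocol 1.1, which is not a rate for this treated population. No dropout is assumed.

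**3. The plan's own figure.** Worsening hazards are −ln(0.55) = 0.598 and −ln(0.75) = 0.288 per year; HR = 0.288/0.598 = 0.481. Events = 4(2.576 + 1.282)²/(ln 0.481)² ≈ 112, against the stated 113. The inputs are read correctly.

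**4. Closed form: equal death hazards, death independent of worsening.** With follow-up uniform on 1 to 2.5 years, P(event) = 1 − (e^−λ − e^−2.5λ)/(1.5λ), and mean time at risk is P(event)/λ.
- Mean time on TtCW: placebo 0.637/0.598 = 1.07 years; active 0.391/0.288 = 1.36 years.
- All-deaths rule: deaths are equal in both arms, so the death-rate ratio is 1.065/1.359 = 0.78 although the truth is 1.00.
- First-event rule: the rate ratio stays 1.00. True mean follow-up is 1.67 years at 0.05 per year and 1.51 at 0.1625. The share of deaths lost is 1 − 1.212/1.671 = 27% and 1 − 1.212/1.512 = 20%, where 1.212 is the two-arm mean on TtCW.

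**5. Simulation, true mortality HR 1.00** (10,000 trials per cell, log-rank at two-sided 0.05, nominal 2.5% per side):

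| Rule | Worsening and death | HR | False significance at 0.05 / 0.10 / 0.1625 per year |
|---|---|---|---|
| All deaths on TtCW | independent | 0.79–0.80 | for drug: 7.0 / 10.6 / 13.8% |
| All deaths on TtCW | shared gamma frailty, variance 1 | 0.82–0.83 | for drug: 5.9 / 7.8 / 11.6% |
| First-event deaths | independent | 0.99–1.01 | about 2.5% each side |
| First-event deaths | shared gamma frailty, variance 1 | 1.23–1.26 | for placebo: 4.5 / 6.6 / 8.8% |

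Repeat runs of the first row gave up to 15.3% at the highest death rate. The hazard ratios apply only if the Cox model also uses TtCW. Stage 3 may be tested at a smaller carried-forward value. At 0.05/3 = 0.0167 (0.8% per side), the first row becomes 2.5 / 4.6 / 6.8%.

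**6. When the drug affects death** (assumed rates, large-sample HRs):
- No effect on worsening (35% in both arms); death 0.05 per year before worsening, then 0.20 (placebo) versus 0.40 (active) after it. True HR 1.50; all-deaths about 1.45; first-event about 1.0.
- Planned effect on worsening; death 0.05 before and 0.25 after it in both arms. True HR 0.74; all-deaths 0.63; first-event 1.00.
- Planned effect on worsening; death 0.05 before, then 0.20 versus 0.40 after. True HR 1.10; all-deaths 0.91; first-event 1.01.

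**The case against.** **The intent is clear, and the SAS blocks are templates.** Four places in the SAP and one in the protocol state the mortality follow-up or censoring, and the printed code has other slips (SAP 6.13.1 declares one subject variable and uses another). SAP 6.12.7 already runs each component, death included, on its own dates. All of this stands, and harm arises only if the line is run as printed. But 6.14.5 commits to using that code. The 6.12.7 death analysis is no substitute, because it is supportive and SAP 6.12.1 censors it 90 days after the last visit. The pre-unblinding addendum on data conventions (SAP 6.2) could correct the line but is not said to.

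**The direction of bias.** A reader might infer that the first-event rule always works against the drug, or that neither rule misleads when the drug leaves worsening unchanged. Neither holds in general. The first is shown only for equal death hazards with shared frailty; in the last example of step 6 the rule hides harm. The first example of step 6 refutes the second.

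**The Cox model and the formal test.** A reader might infer that the hazard ratio is wrong too, or that the source of the Stage 3 p-value and the handling of treprostinil use are open. The documents do not support this. No Cox time variable is printed. SAP 6.12.6 and 6.13.2 take the p-value from the log-rank test and the hazard ratio from Cox, and 6.14.5 reads the same way. SAP 6.9 requires treprostinil use as a covariate in every efficacy analysis. At most, one confirming sentence would help.

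**Conclusion.** The mortality program in SAP 6.14.5 is wrong as written: it contradicts the text of its own section, and no choice of status repairs it. It is probably an uncorrected copy of the 6.12.6 program. The documents do not show that a biased mortality result would be reported, nor in which direction.

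Under equal death hazards of 0.05 to 0.1625 per year, independence and the planned worsening rates, the all-deaths rule gives an HR of about 0.8 and roughly 7% to 15% false significance for the drug. The first-event rule is unbiased there but loses 20% to 27% of deaths. With shared frailty and equal hazards, it is biased against the drug. If the drug changes death after worsening, it misses that effect. Death rates and correlations are assumptions throughout.

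The false-significance rates apply only once the Stage 3 mortality test is reached, and its place in the order is not yet set (SAP 6.10.3). The primary and key secondary endpoints are untouched. It should be corrected before unblinding.

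**What to change.** - Set one mortality cut-off, the formal study close, for deaths and survivors alike. Otherwise deaths collected after close would count while survivors are censored at close.
- TtDeath = the earliest of date of death, date last known alive (if not known dead) and the cut-off, minus date of randomization, plus 1.
- death = 1 for any death on or before the cut-off, whether before or after worsening; otherwise 0.
- Replace the time statement in 6.14.5 with `time TtDeath * death(0);`. Use the same two variables in the Cox model, with treprostinil use included as SAP 6.9 already requires.
- Optionally, add a sentence confirming that the stratified log-rank gives the Stage 3 p-value and Cox the hazard ratio and interval, as in 6.12.6 and 6.13.2.

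The cost is one line of code, two derived variables and a written rule. The vital-status data are already to be collected, and the pre-unblinding addendum in SAP 6.2 can carry the change.
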